#### **4.3.2. Drug Accountability**

Subjects will be instructed to bring the used preparation components when they return for colonoscopy to determine compliance. Failure of a subject to return preparation components does not constitute a protocol violation. The staff members will perform drug accountability by counting any remaining BLI4700 tablets.

Returned study preparation materials must be accounted for on drug inventory log and will be returned to the Sponsor at the completion or termination of the study, unless instructed otherwise by the Sponsor.

#### **4.4. Follow up of Adverse Events and Laboratory Results**

Subjects who have ongoing adverse events related to the study preparation (except for those expected symptoms for which the subjects are prompted in their questionnaire) or abnormal laboratory values from Visit 2 blood draws that the investigator feels are clinically significant will return approximately 7 days following colonoscopy. Subjects with prior clinically significant abnormal laboratory values should undergo repeat testing. Subjects returning due to ongoing adverse events related to study preparation should be assessed to determine if the event has resolved or is clinically stable.

#### 4.5. Tabulated Study Procedures

The following graphically depicts the flow of study procedures at each visit.

Procedures	Visit 1 Screening	Day before colonoscopy	Visit 2 Day of colonoscopy
Informed Consent	X		
Inclusion/Exclusion Criteria Review	X		
Medical History	X		
Physical Examination / Vital Signs	X		X
Review of Concomitant Medication	X		X
Blood Collection for Laboratory Testing	X		X
Urine Pregnancy Test (if applicable) 	X		
Dispense Drug	X		
Instruct Subject	X		
Dispense Preparation Questionnaire	X		
Subject Begins Following Dietary Restrictions		X	
Subject Takes Dose 1 of Preparation – approximately 8 hours prior to colonoscopy			X
Subject Takes Dose 2 of Preparation – 4 hours after starting Dose 1			X
Subject Completes Preparation Questionnaire			X
Subject Completes Symptom Scale and Preference Questionnaire 			X
Drug Accountability			X
Colonoscopy performed with Intra-procedural Safety and Efficacy Grading 			X
Collect and assess adverse event data 			X

 refer to Section 4.7    to be dispensed and completed at Visit 2, prior to colonoscopy

Colonoscopies will be recorded at selected research centers for transmission to sponsor

Subjects with ongoing preparation-related AEs/clinically significant lab results may need to return on follow up Day 7

## 4.6 Physician Assessments

### 4.6.1 Segmental Cleansing Assessment

During the exam, the colonoscopist will rate each colon segment (proximal, mid, distal) using the following scale:

Score	Grade	Description
1	Poor	Large amounts of fecal residue, additional bowel preparation required
2	Fair	Enough feces even after washing and suctioning to prevent clear visualization of the entire colonic mucosa.
3	Good	Feces and fluid requiring washing and suctioning, but still achieves clear visualization of the entire colonic mucosa.
4	Excellent	No more than small bits of feces/fluid which can be suctioned easily; achieves clear visualization of the entire colonic mucosa

### 4.6.2 Overall Cleansing Assessment

Following completion of the procedure, the colonoscopist will provide a global rating of preparation quality for the entire colon (inclusive of their perception of all segments) using the scale outlined in Section 4.6.1.

### 4.6.3 Additional Efficacy Measures

In addition, the following data will be collected:

1. Adequacy of preparation according to the colonoscopist. If the preparation was not adequate, the need for re-preparation will be recorded.
2. Start time of colonoscopy.
3. Time of cecal intubation.
4. Completion time of colonoscopy.
5. Volume of water used to improve visualization.

#### **4.7. Pregnancy**

Subjects that are female and of childbearing potential must have a urine pregnancy test done at screening. A positive result will rule out the participation of the subject in the study.

Female study subjects must be surgically sterilized or use oral contraceptives, depot contraceptives, double-barrier method, intrauterine device, or testify that she is monogamous with a vasectomized partner, or practices abstinence and will continue to do so during the duration of study. Subjects practicing abstinence must agree to use an acceptable form of birth control should they become sexually active during the study. Women who are post-menopausal (as defined in this section), or have had a partial or total hysterectomy or tubal ligation are not considered of child bearing potential.

Oral contraceptives, hormone implants, and injections should be stable for at least 1 month before the study, until completion of the study. Subjects are not allowed to change their birth control method during the course of the study.

Menopausal status is defined when menses have been absent for 12 months in a woman of appropriate age (usually 45 to 55 years) who has no other suspected or identified cause of amenorrheas.

If a subject becomes pregnant during the study, the subject must be removed from the study and followed until one month after the end of the pregnancy. A pregnancy will not be recorded as an adverse event.

#### **4.8. Concomitant Medications**

The use of concomitant medication will be recorded from 7 days prior to screening until completion the study, including intravenous fluids administered during colonoscopy.

## **5. ADVERSE EVENTS**

### **5.1. Adverse Event Definition and Reporting**

An Adverse Event (AE) is any untoward medical occurrence associated with the use of a drug in humans, whether or not considered drug related. An AE can therefore be any unfavorable and unintended sign (including a clinically significant abnormal laboratory finding), symptom, or disease temporally associated with the use of a medicinal (investigational) product. Subjects will be queried for any problems they experienced during and after preparation by site personnel. Symptoms on the symptom scale rated as 2 (mild) to 5 (severely distressing) must be reported as an adverse event. Colonoscopy and biopsy findings are not considered adverse events unless considered by the investigator to be related to the preparation or colonoscopy procedure.

Adverse event collection will commence at the time the patient provides informed consent. Subjects that have an ongoing treatment emergent adverse event or clinically significant abnormal laboratory value will be followed up approximately one week after colonoscopy.

Subjects will be instructed to promptly report adverse events to the Investigator. The Investigator will record date/time of report, date/time of onset, description of the adverse event, severity of adverse event, action(s) taken regarding treatment of the event, action(s) taken regarding study participation, duration of adverse event, and the Investigator's assessment of relationship of adverse event to study preparation.

The Investigator should assess the severity of each adverse event using the following categories:

Grade	Severity	Description
1	Mild	Barely noticeable, does not influence functioning causing no limitations of usual activities
2	Moderate	Makes participant uncomfortable, influences functioning causing some limitations of usual activities
3	Severe	Severe discomfort, treatment needed Severe and undesirable, causing inability to carry out usual Activities
4	Life threatening	Immediate risk of death, Life threatening or disabling (Must be reported as serious adverse event)
5	Fatal	Causes death of the participant (Must be reported as serious adverse event)

The Investigator should assess the relationship to study drug for each adverse event using the following categories:

Categories of Attribution:	Description
UNRELATED	There is no evidence of any causal relationship.
POSSIBLE	There is some evidence to suggest a causal relationship (e.g., the event occurred within a reasonable time after administration of the trial medication). However, the influence of other factors may have contributed to the event (e.g., the subject's clinical condition, other concomitant events).
PROBABLE	There is evidence to suggest a causal relationship, and the influence of other factors is unlikely .
DEFINITE	There is clear evidence to suggest a causal relationship, and other possible contributing factors can be ruled out .

## **5.2 Expected Adverse Events**

Because BLI4700 tablets contain the same active ingredient (sodium sulfate) as SUPREP, a similar adverse event profile is expected. In Phase 3 clinical trials, the most frequent adverse events reported by patients taking SUPREP (reported by >3% of patients) included overall discomfort, abdominal pain and distension, nausea, and vomiting.

## **6. SERIOUS ADVERSE REACTIONS AND DISCONTINUATION OF STUDY**

A Serious Adverse Event (SAE) is any untoward medical occurrence that results in at least one of the following outcomes:

- Results in death
- Is life-threatening
- Requires inpatient hospitalization or prolongation of existing hospitalization
- A persistent or significant incapacity or substantial disruption of the ability to conduct normal life functions
- Is a congenital anomaly/birth defect
- Requires medical or surgical intervention to prevent permanent impairment or damage

SAE collection will coincide with the patient beginning the study preparation and will conclude 30 days after colonoscopy. Pre-scheduled or elective surgeries will not be considered serious adverse events. Should a serious and/or unexpected adverse event occur, the Investigator will notify Braintree Laboratories immediately or no later than 24 hours after gaining knowledge of the event. The Investigator will make a decision regarding continuing study participation, and may request input from Braintree Laboratories. The Investigator will be responsible for recommending or providing the patient with appropriate medical therapy. All patients experiencing serious adverse events will be followed until clinically stable.

Braintree Laboratories must be kept apprised of all follow-up information related to serious adverse events. In addition, Investigators must comply with the SAE reporting requirements of the Institutional Review Board with oversight of the study.

Any serious and/or unexpected adverse events that occur during the study will be reported to Braintree Laboratories as follows:

Contact Telephone Numbers:

During Business hours

(M-F, 8:30 am – 5:00 pm EDT)

After hours or weekends

Braintree Laboratories and its medical monitor will review the report and determine whether an FDA Form 3500A will also be completed and sent to FDA.

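### The SAE window in Section 6 (first dose to 30 days after colonoscopy) conflicts with reporting from consent in Section 5.1 and closes before the outcome of a pregnancy followed under Section 4.7 can be known

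*Combined protocol and SAP*

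**What the plan says.** **Start of collection.** Section 5.1 states: "Adverse event collection will commence at the time the patient provides informed consent". Its severity table marks grade 4 as "Immediate risk of death, Life threatening or disabling (Must be reported as serious adverse event" and grade 5 as "Causes death of the participant (Must be reported as serious adverse event". Neither entry is limited to the period after dosing. Section 6 states: "SAE collection will coincide with the patient beginning the study preparation and will conclude 30 days after colonoscopy". Section 6 also asks the investigator to notify the sponsor of a serious or unexpected event within 24 hours of learning of it, and says that such events arising in the course of the study go to the sponsor. Neither of those two sentences mentions the first dose.

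**End of collection.** One of the SAE outcomes in Section 6 is: "Is a congenital anomaly/birth defect". For a subject who becomes pregnant, Section 4.7 says that "the subject must be removed from the study and followed until one month after the end of the pregnancy", and adds: "A pregnancy will not be recorded as an adverse event". Section 8.2 lists pregnancy among the reasons for discontinuation and asks sites to contact the sponsor beforehand where they can.

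**The concern.** The protocol sets two different start points for what is partly the same set of events, and an end point that is too early for one of its own SAE criteria.

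The pre-dose interval is not empty. Study drug is dispensed at Visit 1, and subjects take it at home before they return. The only scheduled adverse event query is at Visit 2 (Section 4.5). A spontaneous report from the subject, which Section 5.1 asks for, is therefore the main way for a screening-period event to reach the site before dosing. The protocol should not leave it unclear whether the site then sends a life-threatening event to the sponsor as an SAE.

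For pregnancy, the plan requires the follow-up that would reveal a birth defect but stops collecting SAEs first. What is at stake is consistent safety reporting of rare events. No efficacy result is involved.

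**Working it through.** 1. **The plan's own figure.** Section 3.3 allows up to 30 days from screening to colonoscopy and a conditional visit 7 days after it: 30 + 7 = 37 days, the stated maximum participation. It reproduces.

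2. **Gap at the start.** Consent is at Visit 1 (Section 4.1). Dose 1 is about 8 hours before colonoscopy, on the same day (Sections 4.2 and 4.5). The gap between the two start points is therefore the screening interval: from about 4 days (the scheduling target in Section 4.3) to about 30 days. For 60 treated subjects the upper limit is 60 × 30 = 1,800 subject-days. That is time exposed to the conflict, not a count of events. Consented subjects who are never dosed add to it, but the protocol gives no number for them.

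3. **A grade 4 or 5 event in that gap, text by text.**

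| Text | Answer |
|---|---|
| 5.1, start of AE collection | collected |
| 5.1, severity table | report as SAE |
| 6, collection window | outside SAE collection |
| 6, notification and reporting sentences | report to sponsor; no first-dose limit |

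Section 6 thus disagrees with Section 5.1 and also with itself.

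4. **Close of the window against birth.** The window closes at most 30 + 30 = 60 days after screening. The documents give no gestation length, so two assumptions are needed: conception no earlier than 14 days before the negative screening test, and 140 to 280 days from conception to birth.
   - Time since conception at close: at most 60 + 14 = 74 days.
   - Earliest birth after close: 140 − 74 = 66 days. With the longest gestation: 280 − 74 = 206 days. Later conception lengthens both, day for day.
   - Sensitivity: a birth at 140 days falls inside the window only if conception was at least 140 − 60 = 80 days before a negative test.

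   Only a prenatal finding, or one made after an early loss, could fall inside the window.

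5. **Length of the pregnancy follow-up.** Assume term birth at 38 weeks (266 days) and take one month as 30 days: 266 + 30 = 296 days from conception. With conception between 30 + 14 = 44 days before colonoscopy and 7 days after it, follow-up ends 296 − 44 = 252 to 296 + 7 = 303 days after colonoscopy, or about 8 to 10 months. SAE collection ends at 30 days.

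6. **Effect on the analysis.** Sections 9.1 and 9.2 restrict the safety analysis to subjects who took preparation, and summarise events by treatment emergence. Moving the SAE start date does not change which events are treatment-emergent. A subject who has an SAE and is never dosed appears in none of the planned safety analyses, with or without the change.

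**The case against.** The case on the other side has several parts, and much of it limits how far the point can be taken.

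- **Sponsor notice before dosing.** A reader might infer that the sponsor would get no 24-hour notice of a pre-dose event. Section 6 does not say that. Its notification and reporting sentences have no first-dose limit, so the section is unclear rather than prohibitive.
- **Hospitalization.** A reader might extend the conflict between Sections 5.1 and 6 to any pre-dose hospitalization. Section 5.1 makes only grades 4 and 5 reportable as SAEs; hospitalization is a criterion in Section 6 alone. Below grade 4, those two sections do not conflict.
- **Route for pregnancies.** It would be too strong to say that a pregnancy has no route to the sponsor. Section 8.2 gives one. It is conditional, has no deadline, and does not extend to the outcome of the pregnancy.
- **No single rule.** The protocol nowhere says in one sentence that grade 4 and 5 events from consent are SAEs, and Section 5.1 defines an adverse event by its association with drug use. This is arguable, but collection from consent would have little purpose if no pre-dose event could qualify.
- **Small consequences.** Pre-dose events are still collected as adverse events, and the investigator can exclude or withdraw a subject at discretion. Contraception and a negative screening test make pregnancy unlikely. All of this stands, and it argues for a modest weight.

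None of it removes the incompatible start points or links the pregnancy follow-up to SAE reporting.

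**Conclusion.** The point holds as an inconsistency in safety reporting. For grade 4 and 5 events between consent and first dose, up to about 30 days per subject, the protocol's sentences do not agree, and compliant sites could handle the same event differently. A reader might conclude that such events would be classified wrongly. The documents support only that they could be classified inconsistently, since Section 5.1 itself identifies them as serious.

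For pregnancy, the outcome would still be observed under Section 4.7. The gap is that nothing says an anomaly found there is an SAE once the 30 days have passed. The margin of at least 66 days between close and birth rests on the two assumptions about conception and gestation; the conclusion changes only if conception came about 80 days or more before a negative test.

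Few events are expected in a pilot of up to 60 subjects, and the planned treatment-emergent summaries are unaffected. The change is still worth making, because the written window would leave a pre-dose life-threatening event, or a birth defect found in required follow-up, outside SAE collection.

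**What to change.** Reconcile Sections 4.7, 5.1 and 6:

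- In Section 6, start SAE collection at informed consent, to match Section 5.1. Put pre-dose SAEs in a separate listing that includes consented subjects who are never dosed, so that the treatment-emergent tables stay as planned.
- In Sections 4.7 and 6, state that the 30-day limit does not apply to pregnancies under follow-up. Have the investigator notify the sponsor of any pregnancy on the same 24-hour timeline as an SAE, and report a congenital anomaly or other serious outcome as an SAE whenever it is found. Pregnancy itself can remain outside the definition of an adverse event.

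The cost is two or three sentences in an amendment, which needs IRB approval, and a few extra pre-dose SAE forms, most of them for unrelated events.

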## **7. INSTITUTIONAL REVIEW BOARD (IRB) AND INFORMED CONSENT**

IRB review and approval of the study protocol and Informed Consent Form will be obtained prior to initiation of the study. Amendments to the study protocol and consent form generated during the course of the study will also require IRB approval.

## **8. MANAGEMENT OF INTERCURRENT EVENTS**

### **8.1. Modification of Protocol**

Investigators may request an exemption from Braintree Laboratories to enroll a subject with questionable eligibility or to continue a subject with a protocol violation. Note that eligibility criteria exemptions may require pre-approval from the Institutional Review Board. Investigators that continually violate the protocol or commit a serious violation may be subject to termination from the study. The study may be halted if at any time an Investigator or Braintree Laboratories deems the incidence or severity of adverse events to be unacceptable.

## **8.2. Subjects Discontinued from the Study**

Subjects may be dropped from the study for any of the following reasons:

- An adverse event requiring discontinuation (including failure to tolerate study medication).
- Female participants who become pregnant during the study period.
- Major protocol deviation from the study design by the subject that is observed or suspected by the Investigator
- Subject chooses to withdraw from the study, for whatever reason.
- Subject is lost to follow-up.
- The Sponsor initiates an early discontinuation of the study.
- The subject is withdrawn at the discretion of the Investigator.

Braintree should be contacted if possible prior to discontinuation of any subject.

## **9. DATA ANALYSIS**

### **9.1. Study Endpoints - Efficacy**

Primary efficacy will be assessed on the basis of a binary outcome of overall preparation success or failure. The following definition of preparation success and failure will be used:

Definition of successful preparation:

1. Overall Cleansing Assessment by the colonoscopist (Section 4.6.2) of “Excellent” or “Good” and does not satisfy any of the following failure criteria.

Definition of failed preparation:

1. Overall Cleansing Assessment of “Fair” or “Poor” by the colonoscopist.
2. Any subject who did not have a colonoscopy based on the Investigator’s assessment of the cleansing (insufficient fecal output, unclear fecal discharge, etc.) or due to preparation related adverse events.

3. Any subject for whom cleaning was not adequate for evaluation.

Inevaluable Patients:

Subjects who were dispensed a kit but withdrew from the study prior to taking any preparation (including subjects who were disqualified subsequent to Visit 1 based on screening laboratory results) are excluded from the efficacy and safety analyses. Any subject who completely or partially took study preparation but did not have a colonoscopy due to non-preparation related reasons will not be included in the efficacy analyses. All treated subjects will be included in the safety analysis.

Additional efficacy endpoints will include:

- Number (%) of excellent preparations overall and by segment
- Adequacy of cleaning and need for re-preparation
- Duration of colonoscopy
- Volume of intraprocedural water needed to irrigate the colon
- Number (%) of procedures that reached the cecum
- Time to cecum

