**Table 2**  
Preparation Cleansing Score  
BLI800-301/302 Studies

Score	All Patients		301 Patients		302 Patients	
	SUPREP n (%)	MoviPrep n (%)	SUPREP n (%)	MoviPrep n (%)	SUPREP n (%)	MoviPrep n (%)
4 Excellent	200 (53.6%)	168 (44.7%)	86 (44.6%)	72 (37.3%)	114 (63.3%)	96 (52.5%)
3 Good	134 (35.9%)	162 (43.1%)	73 (37.8%)	83 (43.0%)	61 (33.9%)	79 (43.2%)
2 Fair	25 (6.7%)	37 (9.8%)	22 (11.4%)	31 (16.1%)	3 (1.7%)	6 (3.3%)
1 Poor	11 (2.9%)	8 (2.1%)	9 (4.7%)	6 (3.1%)	2 (1.1%)	2 (1.1%)
Mean Score	3.41	3.31	3.24	3.15	3.59	3.47
p value	0.049		0.278		0.050	

Adverse events were also evaluated in the Phase III studies. The only treatment emergent adverse event category with a frequency greater than 3% was gastrointestinal (BLI800 = 4.5% and MoviPrep = 4.3%). The expected symptoms of nausea and vomiting were the most frequent (1.3% each) within the gastrointestinal category. There was no difference between BLI800 and MoviPrep in the frequency of any treatment-emergent adverse events, including those that were gastrointestinal in origin. No clinically significant differences between groups were seen in laboratory testing of serum chemistry and hematology. At the one month follow-up visit, no change in serum creatinine was observed for BLI800 patients.

A smaller Phase III study (n = 136) was conducted comparing the safety and efficacy of SUPREP (in the FDA approved split-dose regimen) to NuLYTELY. In addition to preparation success (as defined above), the blinded colonoscopist also rated the amount of residual fluid and stool in each colon segment. As shown below in Tables 3 and 4, SUPREP was superior to NuLYTELY in overall preparation success, as well as in reducing the amount of residual stool and fluid in most colon segments (most importantly the right colon, a segment with higher miss rates for polyps and flat lesions).

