## **3. STUDY PLAN**

### **3.1. Study Design**

This is an open-label, multi-center study in adult subjects.

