**9.2. Study Endpoints - Safety**

Adverse Events:

All subjects who took preparation in any amount will be included in the safety analysis. All adverse events will be summarized based on the principle of treatment emergence. A sign or symptom will be regarded as treatment-emergent if it was present prior to the first dose and subsequently worsened in severity, or was not present prior to the first dose but subsequently appeared.

In order to define treatment emergence for events with missing start or stop dates the following additional criteria will be used:

- if both the onset and resolution dates for a particular event are missing, then the event is considered treatment-emergent;
- if the onset date for an event is missing and the resolution date falls after the initiation of the first dose, then the event is considered treatment-emergent;

- if the onset date for an event falls after the initiation of the first dose and the resolution date is missing or present, then the event is considered treatment-emergent; and
- if the onset date for an event falls before the initiation of the first dose and the stop date is missing or present, then the event is not considered treatment-emergent.

Adverse events will be collected using MedDRA category designations for body system and preferred term. The number and percent of subjects who experienced each adverse event will be presented in a tabular form.

Vitals Signs and Physical Examination:

Vital signs and physical examination data will be summarized with descriptive statistics.

Laboratory Data:

Results of laboratory tests for the change from baseline (Screening) will be summarized with descriptive statistics.

Symptom Questionnaire Data:

Symptom questionnaire data for individual symptoms for Overall Experience (Stomach Cramping, Stomach Bloating and Nausea) will be presented.

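### Does Section 9.1 let dosed subjects with no colonoscopy and no known reason drop out of the primary success rate?

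*Combined protocol and SAP*

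**What the plan says.** Section 9.1 makes the primary endpoint a binary success or failure of the preparation. For a subject with no colonoscopy it gives two rules.

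- **Failure:** the procedure did not take place because of the Investigator's assessment of the cleansing, "or due to preparation related adverse events".
- **Not evaluable:** a subject who took all or part of the preparation but "did not have a colonoscopy due to non-preparation related reasons will not be included in the efficacy analyses".

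A third failure criterion covers cleansing too poor for evaluation. It does not mention subjects who were never examined.

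Section 8.2 lists reasons for discontinuation. They include an adverse event ("including failure to tolerate study medication"), "Subject chooses to withdraw from the study, for whatever reason", "Subject is lost to follow-up" and the Investigator's discretion. None is mapped to success, failure or not evaluable.

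The safety set in Section 9.2 is wider: "All subjects who took preparation in any amount will be included in the safety analysis". Section 3.1 states the design: "This is an open-label, multi-center study in adult subjects". Section 9.3 allows up to 60 subjects and justifies the number only by the pilot nature of the study.

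**The concern.** Both rules in Section 9.1 need a known and attributed cause. The plan does not define a reason unrelated to the preparation, does not say who judges it when no adverse event is involved, and does not say what happens when the cause is unknown.

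Such cases are conceivable. The symptom form (Section 4.3.1) and the tablet count (Section 4.3.2) are both done at Visit 2. A subject who gives up on the tablets and stays away may leave no adverse event on record, although the preparation was the cause.

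The primary result is a success percentage without a comparator. If ambiguous non-attenders were read as unrelated, they would leave the denominator and the rate would rise. No efficacy analysis on all dosed subjects is planned to show by how much. At stake is a somewhat optimistic estimate of preparation success. Type I error is not at stake, because no test is planned.

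**Working it through.** **1. What the rules do, case by case** (dosed subject, no colonoscopy)

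| Reason | Section 9.1 result |
|---|---|
| Investigator judged the cleansing insufficient | Failure |
| Preparation-related adverse event | Failure |
| Recorded intolerance (grouped with adverse events in Section 8.2) | Failure, by natural reading |
| Known reason unrelated to the preparation | Excluded |
| Unknown reason, or preparation-related with no adverse event recorded | Not stated |

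Only the last row is open. Exclusion requires a reason unrelated to the preparation, and an unknown reason does not meet that condition.

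**2. Size per subject.** The plan has no power or precision figure to reproduce. Inputs are N = 60 (Section 9.3) and success rates among evaluable subjects of p = 82.4% and 97.2%. These are the BLI800 rates in Table 1, borrowed for illustration. With k open cases, the successes number p(60 − k). Excluding the k cases gives a rate of p. Counting them as failures gives p(60 − k)/60. The difference is p·k/60.

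- k = 1: 0.824/60 = 1.4 points; 0.972/60 = 1.6 points.
- k = 3: 3 × 0.824/60 = 4.1 points; 3 × 0.972/60 = 4.9 points.

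With whole subjects, about 90% success (assumed) and exact (Clopper-Pearson) 95% intervals:

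| k | Excluded | Counted as failures | Difference |
|---|---|---|---|
| 1 | 53/59 = 89.8% (79.2 to 96.2) | 53/60 = 88.3% (77.4 to 95.2) | 1.5 points |
| 3 | 51/57 = 89.5% (78.5 to 96.0) | 51/60 = 85.0% (73.4 to 92.9) | 4.5 points |

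The interval for 53/60 is 95.2 − 77.4 = 17.8 points wide, so one disputed case moves the estimate by less than a tenth of that width.

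**3. How many cases to expect.** The documents give no direct figure. The earlier studies in Section 1 offer loose anchors.

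- BLI800, Table 1: 334 + 39 = 373 of 375 analysed, so 2 were left out. 2/375 = 0.5%, or 0.3 per 60. At about 1.5 points each, the expected shift is about 0.5 points.
- MoviPrep, Table 1: 330 + 46 = 376 of 376, so none was left out. Pooled, 2/751 = 0.3%, or about 0.2 per 60.
- BLI800, Table 2: 200 + 134 + 25 + 11 = 370 graded. Failures number 39, against 25 + 11 = 36 graded Fair or Poor, so 3 ungraded subjects were counted as failures.
- The later comparison with NuLYTELY ("A smaller Phase III study (n = 136) was conducted"): Table 3 has 63 + 67 = 130, so 6 of 136 are absent. That is 4.4%, or 2.6 per 60.

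None of these tables gives reasons for the gaps or says whether the missing subjects took any preparation. Undosed subjects would fall under the separate rule in Section 9.1 for those who withdrew before dosing, and would say nothing about this point.

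**The case for a change.** The strongest case for a change is that the remedy is cheap. One sentence could make failure the default when no independent reason is documented, and one extra table could use all dosed subjects. Section 9.2 already sets this kind of default for adverse events with missing dates, so the sponsor knows the technique. Sections 3.4 and 9.1 also leave open whether the two formulations are pooled. With about 30 subjects each (an assumption), one disputed case is worth 0.824/30 = 2.7 to 0.972/30 = 3.2 points.

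What stands is that the text has no default, and that the effect per subject would double in half-size groups. Sampling error grows there too: 26/30 = 86.7% has an exact interval of 69.3% to 96.2%, about 27 points wide.

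The rest is weaker than it looks.

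- These subjects have no cleansing grade, so nobody sorts them knowing their own result. With no control arm, attribution cannot favour one treatment over another.
- Section 5.1 gives the Investigator the judgement on relatedness of adverse events, with defined categories, and tells subjects to report events promptly. Section 8.2 asks that the sponsor be contacted, if possible, before a discontinuation. Reasons are therefore not captured only at Visit 2.
- The earlier data do not show lenient sorting. The 3 ungraded BLI800 subjects were counted as failures.
- A default to failure would not fully settle the hardest case. If a subject never returns, it may be impossible to verify that any tablet was taken. The default also has a downward bias of its own when an unrelated absence goes undocumented.

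**Conclusion.** This is a narrow gap in wording that analysts can fill sensibly, and it does not call for a change to the plan. It concerns only a subject who starts the tablets, has no adverse event recorded, and then disappears or withdraws unexplained in the roughly 8 hours before the procedure (Section 4.2). The rules that are written give no wrong result, and they do not send this subject out of the denominator.

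The likely number is 0 or 1 of 60, at 1.4 to 1.6 points each. The expected shift is about 0.5 points on the BLI800 anchor. On the least favourable anchor, 2.6 subjects per 60, it would be about 4 points (2.6 × 1.5), but that requires every one of those unexplained absences to be a dosed, unclassified case. The plan states no hypothesis, target rate or go/no-go threshold, so no planned decision turns on a shift of this size.

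The conclusion rests on few non-attenders after dosing and on descriptive use of the rate. Reporting any exclusion with its reason, as a study report ordinarily would, lets a reader redo the percentage either way.
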